A total of 1ml (40 mg) will be injected intra-articularly after synovial fluid aspiration 'to dryness' either once (at study entry or 2 weeks after injury) or twice (at both study entry and 2 weeks after injury).

Rational for including pediatric population

The specific reason for enrolling the age group of children aged 14-17 is that these children have a musculoskeletal physiology like adults.

- Their major growth plates are closed.
- These patients may be treated surgically like adult patients with exactly the same surgical preparation, technique and rehabilitation as adults.
- Children, particularly girls, between the ages of 14 and 18 have the highest statistical risk in any population of tearing their Anterior Cruciate Ligament.²⁵
- Children in this age group are particularly vulnerable to the later development of osteoarthritis. Lohmander et al showed that young female soccer players in this age group developed symptomatic knee Osteoarthritis secondary to the ACL injury within 12 years of the injury.²⁴ One could therefore argue that particularly children between completed puberty and 18 years of age have to be the patients requiring most of our concern regarding development of OA.

By slowing the initial inflammatory process after injury and preventing the significant quadriceps muscle shutdown early, we aim to work towards this goal in this trial. We therefore conclude that given the limited risk of local side effects and the potential large benefit that this study would provide to the scientific community and its potential to significantly improve and alter patient care of young individuals suffering ACL injuries it is not reasonable to withhold pediatric patients aged 14-17 from this important trial.

RESEARCH OBJECTIVES OF THE CURRENT STUDY:

The research objectives of this study are:

1. Test the efficacy of Triamcinolone to alleviate knee pain (KOOS, IKDC) and improve patient-reported outcomes (PRO) following ACL rupture in a randomized, placebo controlled, double blinded, clinical trial. Triamcinolone will be administered intra-articularly within 1 week of ACL injury or at 2 weeks after ACL injury, or at both time points and compared with saline control injections. Patients will be evaluated at 5 post-injury time points (1-2 days, 12-14 days, 2 weeks post-op, 4 weeks post-op, 6 months

- post-op, and 24 months post-op) following ACL reconstruction.

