All biomarker analyses in synovial fluid will be performed by co-Investigator [name] (Duke University).

A portion of previously collected samples will be de-identified and shipped on dry ice to Children's National Medical Center at George Washington University where they will undergo the SOMAscan™ assay. The latest version of the SOMAscan assay measures 1,129 protein analytes in only 150 µl of serum. The assay offers exceptional dynamic range, quantifying proteins that span over 8 logs in abundance (from femtomolar to micromolar), with low limits of detection (38 fMol media LOD) and excellent reproducibility (5.1% median %CV) (<http://www.somalologic.com/Technology/SOMAscan-basic-info.aspx>). Once the analyses are complete any remaining samples at National Medical Center will be destroyed. At no time will anyone at Children's National Medical Center have access to subject identifiers or any other subject data.

Randomization: Patients will be randomized into one of four groups, and there will be 17 subjects per group.

- Group 1: will receive injection of Triamcinolone (40 mg) at time point 1 (1-2 days post injury) and saline placebo at timepoint 2 (12-14 post injury).
- Group 2: will receive a saline placebo injection at time point 1 (1-2 days post injury) and 40 mg Triamcinolone at time point 2 (12-14 days post injury.)
- Group 3: will receive two consecutive injections of 40 mg Triamcinolone, the first at time point 1 and the second at time point 2.
- Group 4 (control group): will receive two consecutive injections of saline placebo. The first at time point 1 and the second at time point 2.

Duration of Patient Enrollment: All subjects enrolled in the study will be followed for six months. Those subjects enrolled at the University of Kentucky site will be followed for 24 months, and 20 subjects from the main study will be recruited and enrolled in the extended follow-up MRI sub-study.

Duration of Study: Study duration will be 36 months from the commencement date. This duration may be extended to reach desired enrollment.

Data Safety and Monitoring Board (DSMB) - A DSMB consisting of 5 individuals (will monitor the study semi-annually and review reportable adverse events to the FDA as well as Vanderbilt and University of Kentucky Institutional Review Boards (IRBs). One of these members will maintain the allocation strategy, available upon request from the DSMB.

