The power calculations include several caveats. The power calculation was performed based upon the use of a IL-1 receptor antagonist. There is no clinical data available in a young patient population with knee ligament injuries regarding their pain improvement after cortisone injection. The IL1RA data is the most comparable. Cortisone is a wider spectrum anti-inflammatory than IL-1RA and thus may have a larger effect on pain control that may be longer lasting. In that case our study may be over-powered. First, for purposes of power calculation, we have not assumed a full repeated measures analysis, but have instead analyzed change from baseline at a single time point. Second, we note that in trials such as this, the power of a non-parametric analysis is never much lower than its parametric analog (the "asymptotic relative efficiency" of the Wilcoxon test is at least 0.95), leading us to conclude that our parametrically based power calculations should apply with equal force to a non-parametric analysis.

Statistical analyses - Results from a sample of this size may not be normally distributed. Therefore, non-parametric statistical measures may be used. Primary outcome measures evaluating for change in KOOS and IKDC will be assessed at multiple points and will be analyzed for change between groups using Friedman two-way ANOVA for repeated measures. Synovial fluid analyses comparing the three groups at three time points will be analyzed using the Wilcoxon Signed Rank Sum Test with Hochberg corrections for multiple time points. Alternatively, if results are normally distributed or can be transformed (e.g., by log transformation) to meet the criteria for normality for parametric analysis, then repeated measures ANOVA will be utilized comparing treatment groups. P-values of less than or equal to 0.05 will be considered statistically significant. For those subjects enrolled in the extended follow-up sub-study the 24 month time point will be examined as an additional time point. Additionally, correlation analyses will be used to examine the relationship between biomarkers collected at Visits 1-3 and KOOS and IKDC values and MRI findings at 24 month follow-up.

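### On the non-parametric branch, the primary KOOS/IKDC comparison between groups is assigned to Friedman's test, which has no arm term and so does not test triamcinolone against saline

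*Combined protocol and SAP*

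**What the plan says.** The relevant text is the Statistical analyses paragraph under Statistics, Quality Control and Minimization of bias. The wording is the same in all three copies of the protocol in the combined file.

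- The paragraph opens with the non-parametric route: "Results from a sample of this size may not be normally distributed. Therefore, non-parametric statistical measures may be used".
- On that route, the primary measures, change in KOOS and IKDC at several time points, "will be analyzed for change between groups using Friedman two-way ANOVA for repeated measures".
- The only other non-parametric test named there is for a different outcome: "Synovial fluid analyses comparing the three groups at three time points will be analyzed using the Wilcoxon Signed Rank Sum Test".
- If the data are normal or can be transformed to be so, "then repeated measures ANOVA will be utilized comparing treatment groups".

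The design is in the Randomization paragraph: "Patients will be randomized into one of four groups, and there will be 17 subjects per group". The arms are parallel and unmatched, and Group 4 receives saline twice. Objective 1 asks for triamcinolone given within 1 week, "or at 2 weeks after ACL injury, or at both time points and compared with saline control injections". No section names any other non-parametric comparison between arms for KOOS or IKDC.

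**The concern.** The sentence promises a comparison between groups and names a procedure that does not deliver one. Friedman's test handles one factor within blocks. Treatment arm in this trial is a factor between patients, so it does not enter the usual calculation.

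KOOS and IKDC are collected from acute injury, through surgery, to six months, so change over visits is to be expected whatever the drug does. A significant Friedman result would correctly show that change. If it were reported as a result between groups, which is how the plan words it, it would be an efficacy claim without a comparison behind it. If the analyst noticed and chose another test, the primary test would be chosen outside the plan, possibly after seeing the data.

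**Working it through.** **The plan's own figures.** No figure in the plan belongs to the Friedman test. Its power figures are for change from baseline at a single time point, treatment against placebo. Whether they reproduce is a separate question, and this point does not depend on them.

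**Step 1: the formula, patients as blocks.** Inputs: n = 4 × 17 = 68 patients (Randomization) and k = 6 visits (Visits 1 to 6). Each patient's six values are ranked 1 to 6, and R_j is the sum of the ranks at visit j over all patients:

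Q = 12 / [n k (k+1)] × Σ R_j² − 3 n (k+1) = (12 / 2856) × Σ R_j² − 1428, with k − 1 = 5 degrees of freedom.

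Nothing in Q carries an arm index. Relabelling patients between arms leaves every R_j unchanged. Adding a constant to all of one patient's values leaves that patient's ranks unchanged.

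**Step 2: direct check.** On one simulated data set Q = 6.134 (p = 0.293). Adding 5 SD to every visit of all 51 active-arm patients gave the same Q and p, as did permuting patients across arms. On another data set the Friedman p-value was 0.0000513 before and after a label shuffle, while Kruskal-Wallis on Visit 1 to 6 change moved from 0.903 to 0.620. Steps 1 and 2 establish the point and need no assumption about recovery or correlation.

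**Step 3: illustration with no drug effect.** Assumed, because the documents give none of it: normal data in SD units, linear recovery common to all arms, and a stated within-patient correlation; 2,500 to 4,000 simulated trials per case, alpha 0.05.

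| Recovery, correlation | Friedman rejects |
|---|---|
| none, equal 0.5 | 5.6% |
| 0.5 SD, equal 0.3 / 0.5 / 0.7 | about 82 / 95 / 99.8% |
| 0.5 SD, AR(1) 0.3 / 0.5 / 0.7 | about 64 / 67 / 76% |
| 1.0 SD, AR(1) 0.3 to 0.7 | at least 99.7% |

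Kruskal-Wallis on Visit 1 to 6 change, which does contain arm, stays at 3.8 to 5.4% throughout.

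**Step 4: does Friedman respond to a drug effect?** Yes, but only through pooled change over visits. Take a 0.65 SD benefit from the first active injection (Groups 1 and 3 from Visit 2, Group 2 from Visit 3). With no recovery Friedman rejects in 95% of trials at equal correlation 0.5 (71 to 99.8% over the correlations tried). With 0.5 SD recovery it rejects in about 99% or more. At equal correlation 0.5 and 0.5 SD recovery that is about 95% without drug and about 100% with it, so the result cannot be attributed to an arm.

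**Step 5: the other layout, visits as blocks and arm medians as conditions.** This compares arms, but the blocks are the same patients measured again, and the test assumes independent blocks. Rejection with no drug effect:

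| Scoring | Equal correlation 0.3 to 0.7 | AR(1) |
|---|---|---|
| raw medians, six visits | about 21 to 62% | about 11% at 0.3 |
| change from Visit 1, five visits | about 35 to 36% | about 39 to 49% at 0.3 to 0.7 |

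The narrow 35 to 36% is not a sign of robustness. Under equal correlation, subtracting Visit 1 makes any two change scores correlate at exactly 0.5, whatever the original correlation.

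**The case against.** The strongest reply is that the branch is optional, the intended comparison is stated plainly, and only the name of the procedure is wrong; a competent analyst would substitute a suitable test. It stands that the route is optional and that the repeated measures ANOVA alternative compares treatment groups. But the plan puts the non-parametric route first because it doubts normality at this sample size, and it names no substitute for KOOS or IKDC.

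A second reply is that the percentages rest on invented recovery curves. That is fair. Linear improvement is a simplification when Visit 3 is the day of surgery and Visit 4 falls 1 to 2 weeks later. The percentages show scale only; the missing arm term does not depend on them.

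A reader might infer more than the documents support:

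- *That the whole primary analysis is invalid.* It is not; the parametric branch is sound on this point.
- *That Friedman cannot see a drug effect, or that a significant result is a false positive.* Neither is right. It responds to change over visits from any source and detects it correctly. The error lies in reading that as a difference between groups.
- *That the biomarker test is equally wrong.* The wording there merges signed-rank, which needs pairs, with rank-sum, which can compare independent arms. It is ambiguous, not demonstrably wrong. Any familywise error figure for the biomarkers would rest on contrasts the plan does not name, and is no evidence for the main point.

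**Conclusion.** The point holds for the non-parametric branch. Followed as written, the primary KOOS/IKDC analysis there does not test objective 1. In the usual layout, arm does not enter the statistic. In the other layout, arms are compared with a false-positive rate well above 5%: about 11% in the mildest case tried and about 62% in the worst. The structural conclusion rests on the definition of the test and on four unmatched parallel arms. The sizes rest on the assumed recovery, correlation and normal data. It should be corrected before unblinding because it concerns the primary outcome, although the parametric branch is unaffected.

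**What to change.** Replace the Friedman sentence with a rank-based analysis that contains arm, for example:

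> If the non-parametric analysis is used, KOOS and IKDC at [visit or visits named by the sponsor before unblinding] will be compared between each of Groups 1, 2 and 3 and Group 4 by rank ANCOVA adjusting for the Visit 1 value (or by Wilcoxon rank-sum tests of change from Visit 1), with Hochberg correction over the three contrasts.

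No preliminary Kruskal-Wallis test is needed. Hochberg already controls the error over the three contrasts (simulated familywise error about 4%). Requiring both lowers power from about 35/47/71% to about 28/40/64% at equal correlation 0.3/0.5/0.7.

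The sponsor must choose the visit. The plan names no primary visit: its pilot effect sizes are for days 0 to 4 and it expects early benefit, yet "All subjects enrolled in the study will be followed for six months". Two checks bear on the choice:

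- Group 2 "will receive a saline placebo injection at time point 1 (1-2 days post injury) and 40 mg Triamcinolone at time point 2", so a contrast at Visit 2 carries no earlier drug exposure in that group.
- If Visit 6 is chosen, confirm that KOOS and IKDC are collected then. The visit list says so, but in the last copy of Appendix A those rows look blank at Visit 6, possibly only a table-reading artefact.

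The cost is wording; data and software are unchanged. The plan should state the downside. At a 0.65 SD benefit, rank-sum tests of Visit 1 to 6 change with Hochberg have about 35/47/71% power for at least one arm (equal correlation 0.3/0.5/0.7), and about 26% at AR(1) 0.3. Adjustment and averaging help. At equal correlation 0.5, Kruskal-Wallis on that change has 40 to 42% power, rank ANCOVA at Visit 6 has 52 to 53%, and rank ANCOVA of the Visit 3 to 6 mean has 83 to 85%. These three show direction and are not the power of the Hochberg procedure.

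Separate minor wording: say rank-sum for the synovial fluid comparison between arms, and reconcile its three groups with the four randomised. The correction above covers one outcome at a time; multiplicity across KOOS subscales and IKDC needs its own rule.

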2. Determine if intra-articular Triamcinolone therapy improves levels of a panel of inflammatory (cytokine), meniscus and cartilage metabolism and oxidative stress biomarkers as measured in synovial fluid from patients at relatively short-term time points after ACL injury (1-7 days, 10-17 days after injury and at time of surgery). Biomarkers to be tested include IL-1 α , IL-1 β , Collagen type I (NtxI) and collagen type II (CTXII) breakdown products, cartilage oligomeric protein (COMP) and glycosaminoglycan (GAG) and Xanthine Oxidase. Additionally, the change in IL-1 α and IL-1 β levels in the Triamcinolone treated and placebo individuals will be evaluated specifically for association with pain and function outcomes.

RESEARCH OBJECTIVES OF EXTENDED FOLLOW-UP SUB-STUDY:

1. Determine if joint health as evaluated by MRI at 24 months following ACL injury is influenced by the initial treatment with Kenalog. Two years following ACL injury MRI analysis using standardized T2-mapping will be performed on 10 control subjects and 10 subjects who have received Kenalog injections.

INVESTIGATIONAL PLAN

Description of Overall Study Design and Plan (See Figure 1 for study timeline)

This study is a multicenter, randomized, placebo controlled, double blinded, clinical trial. This trial will enroll 68 subjects between the ages of 14 and 33. This trial will be conducted at two clinical centers, the University of Kentucky and Vanderbilt University, as well as established criteria and support of the Multicenter Orthopaedic Outcome Network (MOON). A sub-study involving extended follow-up of patients, 24 months post-surgery will occur at the University of Kentucky clinical center only. This sub-study will involve 20 subjects of the initial University of Kentucky cohort returning for one additional follow-up MRI.

Description of observations and measurements to be made in this study:

[figure not shown]

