Sample Size and Power Analysis - We used the VAS and WOMAC data from Chevalier et al. as the template for power calculations [4] and the change in KOOS pain and ADL from our study. Chevalier reported a 53% response rate by VAS. Response was defined as a 50% improvement in VAS pain score from baseline. We observed comparable differences in our study (20-30% between outcomes in the IL-1Ra and placebo groups); therefore this dataset is reasonable to estimate study power. Based upon the change in VAS pain score in the Chevalier study, and conservatively estimating a placebo response rate of 30%, the effect size was 0.47 for a dichotomous outcome. At this effect size power for a sample size of 17/group is reasonable (65%) for the weakest possible outcome (i.e., one that only generates a "yes" or a "no" for each patient). Moreover, power is excellent for the continuous KOOS outcomes. With 17 patients per group we achieve 90% power for effect sizes of approximately 0.77 and 80% power for effect sizes of approximately 0.65. These latter effect sizes are in standard deviation multiples. So, for example, if the standard deviation of the VAS is approximately 20, and we expect an improvement of approximately 20 units in the intervention group, we can tolerate an improvement of approximately 7 units in the placebo group and still have 90% power (i.e. the effect size is $(20-7)/20 = 0.65$). Moreover, using the effect size standard benchmarks of 0.50 as moderate and 0.80 as large, we will be powered to detect moderate-to-large effects of the intervention, which is consistent with intuition for a study of this size. Power calculations based on our pilot KOOS data confirm this estimate. The change in KOOS (days 0-4) comparing treatment and placebo groups yielded an effect size of 0.62 for pain and 1.08 for ADL. At a

group size of 17 we will have 80% power to detect a difference in KOOS pain and >99% power to detect a difference in KOOS ADL.

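### KOOS and IKDC analyses need a complete row of visits per subject and state no missing-data or sphericity provision; the arm-by-visit test could run at about 5 to 12% instead of 5%

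*Combined protocol and SAP*

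**What the plan says.** The rules are in Statistical analyses, under Statistics, Quality Control and Minimization of bias. I use the last copy of the protocol in the combined document, in which the extended sub-study is MRI only.

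- Change in KOOS and IKDC is the primary outcome, assessed at several visits, and "will be analyzed for change between groups using Friedman two-way ANOVA for repeated measures".
- If results are normal or can be transformed, "then repeated measures ANOVA will be utilized comparing treatment groups". This sentence follows the one on synovial fluid; I read it as covering KOOS and IKDC too.
- "P-values of less than or equal to 0.05 will be considered statistically significant".
- For subjects enrolled in the extended follow-up sub-study, "the 24 month time point will be examined as an additional time point".

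On size and follow-up: "This trial will enroll 68 subjects between the ages of 14 and 33" (Description of Overall Study Design and Plan), "Patients will be randomized into one of four groups, and there will be 17 subjects per group" (Randomization), and "Those subjects enrolled at the University of Kentucky site will be followed for 24 months" (Duration of Patient Enrollment). The sub-study is 20 Kentucky subjects, 10 control and 10 given Kenalog.

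Subjects who decline reconstruction stay in the study (Knee Aspiration; Appendix A, footnote 5), although Visits 3 to 5 are timed from surgery. A subject who discontinues before Visit 5 is left out of the efficacy analysis and replaced (Early Termination of Subjects from Study).

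No missing-data method, sphericity check or epsilon correction is stated. Nor are the site split, a dropout rate or a within-subject correlation.

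**The concern.** Two properties of the named methods do not fit this visit schedule.

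First, both need complete blocks. One missing score removes a subject's whole row, including scores soon after injection, when the drug effect is expected. The replacement rule covers only discontinuation before Visit 5. It does not cover a missed visit by someone who stays, a subject who is not operated on, or loss at 6 months.

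Second, the within-subject F tests of repeated measures ANOVA assume sphericity. Visits run from days after injury, through an operation, to 6 months. Equal variances of all between-visit differences are implausible there, and no correction is named. The arm-by-visit test is the one that addresses a drug effect that changes over time, so its error rate matters.

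The 24-month sentence adds a third uncertainty. If that visit joined a complete-row model, everyone without a 24-month score would leave the analysis.

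**Working it through.** **Plan's own figure.** With 17 per group, "we achieve 90% power for effect sizes of approximately 0.77 and 80% power for effect sizes of approximately 0.65". For a two-sample, two-sided t test the noncentrality is d × √(n/2). With d = 0.65 and n = 17 it is 0.65 × √8.5 = 1.90 on 32 df, which gives 45% power; d = 0.77 gives 59%. One-sided, the figures are 58% and 71%. The stated power does not reproduce. That is a separate matter, and nothing below depends on it.

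**Complete rows to 6 months.** Inputs: 4 arms × 17 = 68, with five post-baseline visits (Visits 2 to 6). The missed-visit rate m is my assumption. Complete per arm = 17 × (1 − m)^5.

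| m | Complete per arm |
|---|---|
| 3% | 14.6 |
| 5% | 13.2 |
| 10% | 10.0 |
| 15% | 7.5 |

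At 5% the total is 68 × 0.95^5 = 68 × 0.774 = 52.6, about 53. If every loss before Visit 5 were a discontinuation and were replaced, two factors would remain: 68 × 0.95² = 61.

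**Size of the arm-by-visit test.** F = MS(arm × visit) / MS(visit × subject within arm). Six visits give (4 − 1)(6 − 1) = 15 and (68 − 4)(6 − 1) = 320 df; seven visits give 18 and 384. The table shows null simulations with 4 × 17 complete subjects, nominal 5%, no correction. Ranges are across independent runs of at least 10,000 trials in most cases; the Monte Carlo standard error near 8% is √(0.08 × 0.92 / 10,000) = 0.27 points.

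| Assumed correlation | Visits 1–6 | Plus 24 months |
|---|---|---|
| Compound symmetry | 4.9–5.2% | 4.9–5.1% |
| AR(1) 0.3 | 5.4–5.9% | 5.9% |
| AR(1) 0.5 | 6.8–7.3% | 7.2–7.7% |
| AR(1) 0.7 | 7.9–8.8% | 9.4–9.5% |
| AR(1) 0.9 | 10.3–11.4% | 11.6% |

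Sample size is not the cause. With seven visits and AR(1) 0.7 the rate is 9.5% at 17 per arm, 9.3% at 8 to 9 and 9.6% at 5. The highest value in any setting was 12.0%. With a Greenhouse-Geisser correction the test ran at 4.2 to 6.0% at 17 per arm.

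**If 24 months entered a complete-row model.** The documents leave two candidate populations.

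- All Kentucky subjects. Site share alone gives 68 × 0.30 / 4 = 5.1 per arm up to 68 × 0.90 / 4 = 15.3. With 5% missed per visit as well, a 50–75% Kentucky share and 70–90% mail return (all assumed), 52.6 × 0.50 × 0.70 = 18.4 up to 52.6 × 0.75 × 0.90 = 35.5 subjects remain, or 4.6 to 8.9 per arm.
- The 20 sub-study enrollees: 10 controls and 10 / 3 = 3.3 per Kenalog arm on average.

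**The case against.** The strongest reply is that the plan never says the 24-month visit enters the whole-trial model. The sentence is confined to sub-study enrollees and says only that the visit will be examined. A reader might infer that the plan cuts the trial to 5 to 9 per arm by deleting every Vanderbilt subject. The documents do not support that: it is one reading of an ambiguous sentence, and the count multiplies three rates the plan does not give. Nor is it settled that Vanderbilt lacks 24-month scores. Duration of Patient Enrollment implies it, but objective 1 lists 24 months with no site limit, and the mailed Visit 7 carries none.

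A reader might also infer that adding 24 months causes the inflation, or that 7 to 9% is a fixed figure. Neither is so. The inflation is present with Visits 1 to 6 alone, and under compound symmetry there is none.

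The sphericity point is also limited in scope. It does not touch the between-arm main effect, and the plan does not name the interaction as its primary test. Friedman, the first-named method, has no arm-by-visit test, so the simulated rates say nothing about it. For the same reason it offers no substitute for that test.

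All of this stands, and it makes the figures conditional. What remains is that both methods need complete rows, that the protocol itself retains subjects who will lack visits, and that a named analysis can miss its 5% level with no correction stated.

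**Conclusion.** The point holds in conditional form, as a should-fix. The complete-row requirement and the absence of any missing-data or sphericity provision follow from the text and the methods, with no assumed figure. The sizes rest on assumptions: about 7.5 to 14.6 complete subjects per arm to 6 months for 15% to 3% missed per visit, less severe to the extent that losses are replaced discontinuations; and a size of about 5 to 12% for the uncorrected arm-by-visit test as correlation runs from compound symmetry to AR(1) 0.9. The loss at 24 months arises only if that visit is put in a complete-row model. Its extent depends on the unstated site split and return rate, so 4.6 to 8.9 per arm is an example and not a forecast.

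**What to change.** Replace the Friedman and repeated measures ANOVA pair for KOOS and IKDC with one prespecified linear mixed model for repeated measures:

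- REML on all observed visits, with arm, visit, arm × visit, Visit 1 score and centre as fixed effects.
- Unstructured within-subject covariance with Kenward-Roger degrees of freedom, and a named fallback (for example heterogeneous Toeplitz) if it does not converge.
- Arm contrasts reported at each visit.
- A rank-based or transformed sensitivity analysis, since the plan expects possible non-normality.

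State that adding 24 months removes no one from the analysis to 6 months, and that the 24-month contrast rests on Kentucky responders; the model cannot supply scores that were never collected. Reconcile the 24-month sentence with objective 1 and Duration of Patient Enrollment.

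If repeated measures ANOVA is kept, apply a Greenhouse-Geisser correction and leave 24 months out of that model. This repairs the error rate but not the loss of incomplete subjects.

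The cost is changed wording and routine software, with no new data. The downsides are more covariance parameters on 17 per arm (5 × 6 / 2 = 15 for Visits 2 to 6, 6 × 7 / 2 = 21 with Visit 7), a missing-at-random assumption that should be stated, and one extra sensitivity analysis.
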